5.3. Definition of Dose-limiting Toxicities and Maximum Tolerated Dose

5.3.1. Definition of Dose-limiting Toxicities

A DLT is defined as any Grade 3 or higher non-hematological AE unless related to the primary disease, course of the primary disease, complications, or concomitant medications, that occurs during the DLT evaluation period (28 days of Cycle 1), with the exceptions as defined below:

1. The following events will be assessed as DLTs:
 - Grade 4 aspartate aminotransferase (AST)/alanine aminotransferase (ALT)

- Grade 3 AST/ALT lasting ≥ 3 days, Grade 3 AST/ALT with Grade ≥ 2 total bilirubin
- Unable to complete at least 75% of the prescribed doses of DS-3032b in Cycle 1 (28 days) as a result of Grade ≥ 2 events

2. The following events will not be assessed as DLTs:

- Grade 3 fatigue lasting < 3 days
- Grade 3 nausea or vomiting that has resolved to Grade ≤ 2 within 48 hours after antiemetic therapy
- Grade 3 diarrhea that has resolved to Grade ≤ 2 within 48 hours after antidiarrheal therapy
- Alopecia
- Febrile neutropenia
- Transient laboratory abnormalities that do not involve clinical symptoms and do not require continuous treatment (\geq Grade 3 ALP, uric acid, amylase, and lipase, hyponatremia that has resolved within 72 hours after onset, etc.)

The following hematological toxicities will be assessed as DLTs.

- Failure to recover neutrophil count to $\geq 500 /mm^3$ and platelet count to $\geq 20,000 /mm^3$, leading to a delay in starting Cycle 2 for more than 2 weeks

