5.3.2. Definition of Maximum Tolerated Dose

If any of the following completion criteria are met, the MTD will be determined based on comprehensive evaluation of the recommended dose guided by mCRM incorporating the EWOC principle, and safety and PK/PDy information of DS-3032b.

Completion criteria:

- DLT evaluation is completed in at least 15 subjects in the entire study and in at least 6 subjects in the cohort of the dose selected to be the dose for the next cohort by mCRM.
- DLT evaluation is completed in at least 6 subjects in the cohort of the dose selected to be the dose for the next cohort by mCRM, with at least 50% posterior probability for the DLT rate ranging between 16% and 33%.
- DLT evaluation is completed in at least 3 subjects in the cohort of each dose, with no DLTs reported.
- The posterior probability for the DLT rate of 33% or higher in the 90 mg cohort is at least 60%.

5.3.3. Study Treatment to Subjects in Each Cohort and Procedure for Proceeding to the Next Cohort

In the cohort of the first dose, study treatment for the second subject must be started after an at least 1-week interval from the first dose of treatment in the first subject. In the subsequent cohorts, study treatment for the next subject may be started on the following day of the start day of study treatment in the first subject.

If proceeding to the next cohort involves an increase in the dose, study treatment for the first subject in the new cohort will be started after the end of the DLT evaluation period in at least 3 subjects in the ongoing cohort. If a DLT occurs in 2 subjects before registration of the third subject, the dose for the third subject will be reviewed by using the mCRM incorporating the EWOC principle.

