5.4. Enrollment of Additional Subjects

If there is a subject who cannot be evaluated for DLTs because of withdrawal from the study before the end of Cycle 1 for any reason during the study, additional subjects will be enrolled. In other cases where enrollment of additional subjects is considered necessary, whether or not to enroll additional subjects will be considered through discussion between the investigator and the sponsor. The medical expert may join the discussion as necessary.

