11.2.2. Maximum Tolerated Dose Analysis Set

The MTD analysis set will include all subjects who received at least one dose of the study drug but will exclude subjects who have missing data of one or more examination or observation items during the DLT evaluation period for other reasons than adverse drug reactions (worsening of clinical conditions due to progression of the primary disease, AEs for which a relationship with the study drug is ruled out, etc.) and whose DLT evaluation could not be performed appropriately. The MTD analysis set will also include subjects who have experienced DLT in Cycle 1 and subjects who have received the study drug on at least 75% of the specified days in Cycle 1 in the absence of DLT.

Subjects for whom the study treatment is postponed due to a DLT occurring during the DLT evaluation period, and the study treatment is then resumed at a reduced dose will be

handled as those included in the MTD analysis set for the dose level at the first dose of the study drug.

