11.7.2. Prior Distribution of Bayesian Logistic Regression Model

Assuming that BLRM model parameters $\log(\alpha)$ and $\log(\beta)$ follow bivariate normal distribution, a minimally informative prior distribution is set as follows. If other dosing schedules are assessed, each parameter will be set separately based on the information obtained up to that time.

Parameter	Mean	Standard Deviation	Correlation Coefficient
$\log(\alpha), \log(\beta)$	(-1.8999, 1.3484)	(2.2792, 1.3727)	-0.3157

The above parameters for a prior distribution will be calculated as shown below.

- Based on the overseas Phase 1 study (U102), the median probability of the DLT rate was estimated to be 5% and 20% for the 120 mg qd 21/28 day schedule and the 160 mg qd 21/28 day schedule, respectively.
- From the ratio (0.67) of the dosing days in this study to U102, the median probability of the DLT rate is assumed to be 3% and 13% at doses of 120 mg and 160 mg, respectively, in this study.
- Based on the median probability of the DLT rate at the above doses, parameters of the bivariate normal distribution will be calculated to generate vague prior Bayesian intervals (to minimize prior information) using minimal information beta distribution.

11.7.3. Recommended Dose for the Next Cohort by Bayesian Logistic Regression Model Incorporating the Escalation with Overdose Control Principle

The recommended dose in the next cohort is decided based on posterior distribution of the DLT rate at planned doses (90 mg, 120 mg, and 160 mg). After completing DLT evaluation in 3 subjects per cohort in principle, posterior distribution of the DLT rate at each planned dose will be estimated using BLRM based on the results of DLT evaluation and prior distribution set in “[Section 11.7.2 Prior Distribution of Bayesian Logistic Regression Model](#),” and posterior probability of the DLT rate falling under the following four intervals will then be calculated for each planned dose. The following posterior probabilities can also be calculated for other doses than the planned, as long as the dose is more than 1.3 times but not more than 2 times of the dose in the concerned cohort.

- [0, 16%]: DLT rate interval for under-dosing
- (16, 33%]: target DLT rate interval
- (33, 60%]: DLT rate interval for excessive toxicity
- (60, 100%]: DLT rate interval for unacceptable toxicity

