Among the planned doses and additional candidate doses, the dose with posterior probability of 25% for the DLT rate exceeding 33% (probability for excessive and unacceptable toxicity) (according to the EWOC principle) and with the highest posterior probability for the DLT rate being more than 16% and 33% or less (probability for target DLT rate interval) will be chosen as the recommended dose for the next cohort. The EWOC principle will apply from the third cohort. Dose increments for the next cohort should be within the 1.3-fold and 2-fold range.

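### The only listed hematological DLT cannot be read before about Day 43, but escalation, the model update and completion can go ahead at the end of Day 28 with no rule for a pending or late DLT

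*Combined protocol and SAP*

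**What the plan says.** Section 5.3.1 defines DLTs over the 28 days of Cycle 1. Its hematological list has one item: neutrophils and platelets that do not recover to 500 and 20,000 per mm³, "leading to a delay in starting Cycle 2 for more than 2 weeks". Appendix 1 (note a, each subtrial) places DLT evaluation at the end of the 28-day Cycle 1.

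Three decisions depend on that evaluation:

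- **Escalation (5.3.3).** The first subject at a higher dose "will be started after the end of the DLT evaluation period in at least 3 subjects in the ongoing cohort".
- **Model update (11.7.3).** The posterior is computed "After completing DLT evaluation in 3 subjects per cohort in principle". The overdose limit comes in late: "The EWOC principle will apply from the third cohort".
- **Completion (5.3.2, third criterion).** "DLT evaluation is completed in at least 3 subjects in the cohort of each dose, with no DLTs reported".

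Section 11.2.2 includes in the MTD analysis set "subjects who have experienced DLT in Cycle 1". Section 5.4 requires additional enrollment when a subject cannot be evaluated "because of withdrawal from the study before the end of Cycle 1 for any reason". Section 5.5.1 deals with DLT-type toxicity after Cycle 1 only as dose management for the affected subject.

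**The concern.** The plan defines a DLT that its own evaluation point cannot observe. On the 14/28 schedule a subject can take all 14 doses, reach Day 28 with unrecovered counts and have no DLT at that point. About two weeks later the same subject may meet the hematological criterion. By then a higher dose may already have been released, or Subtrial A declared complete.

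Inside the window, marrow toxicity can count only by a narrow and ambiguous route: failing to complete 75% of Cycle 1 doses because of Grade 2 or higher events. That route misses the subject just described. Febrile neutropenia is expressly not a DLT.

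The MTD is part of the primary objective, so misreading one subject affects both the trial's main result and the safety of the next subjects dosed.

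**Working it through.** **Timing.** Cycle 2 Day 1 = 28 + 1 = Day 29. A delay of exactly 14 days is reached on Day 29 + 14 = Day 43; the first day strictly beyond two weeks is Day 44. The escalation gate for the last of three subjects opens on that subject's Day 29, so the gap is 43 − 29 = 14 days. In the first cohort the second subject starts no earlier than the first subject's Day 8, so the gate opens no earlier than the first subject's Day 36 and that subject's gap is 43 − 36 = 7 days. Fourteen days is long enough for the first subject at the next dose to finish a 14-day dosing block if dosing starts at the first opportunity.

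**Model.** From 11.7.1 and 11.7.2: logit π(d) = log α + β log(d/160), with (log α, log β) bivariate normal, means (−1.8999, 1.3484), SDs (2.2792, 1.3727), correlation −0.3157. The posterior is proportional to the prior times the product over doses of π(d)^y · (1 − π(d))^(n−y), integrated on a grid.

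**Plan's own figure.** The prior medians come out at 3.05% at 120 mg and 13.0% at 160 mg, matching the 3% and 13% in 11.7.2.

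**Effect of one late event scored as DLT-free.** Target means a DLT rate above 16% and up to 33%; over means above 33%. Values are for 90 / 120 / 160 mg.

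| Data | P(target) | P(over) |
|---|---|---|
| 0/3 at 90 | 0.04 / 0.08 / 0.16 | 0.02 / 0.04 / 0.17 |
| 1/3 at 90 | 0.29 / 0.28 / 0.22 | 0.31 / 0.48 / 0.63 |
| 0/3 at 90, 0/3 at 120 | 0.02 / 0.04 / 0.15 | 0.00 / 0.01 / 0.11 |
| 0/3 at 90, 1/3 at 120 | 0.17 / 0.30 / 0.29 | 0.05 / 0.15 / 0.44 |

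1. *Third-cohort decision, overdose limit in force.* The 25% in 11.7.3 is read as an upper limit on P(over). With the late event counted (1/3 at 120 mg), 160 mg has P(over) 0.44, is barred, and 120 mg is chosen. Scored as 0/3 it has 0.11, is allowed, and is chosen.
2. *Second-cohort decision, overdose limit not yet in force.* With 1/3 at 90 mg the highest target probability is at 90 mg (nearly tied with 120 mg), and P(over) at 160 mg is 0.63. Scored as 0/3, the highest is at 160 mg, with P(over) 0.17. The step 160/90 = 1.78 is within the 2-fold cap.
3. *Last cohort.* With 0/3 at each dose, P(over) at 160 mg is 0.02 and the zero-DLT criterion is met with 9 subjects. With one late DLT at 160 mg, P(over) is 0.21 and the criterion was not met.

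**How likely is the event?** The documents give no rate. In the overseas solid tumor/lymphoma study (1.3.1), 5 of the 6 subjects with DLTs had thrombocytopenia or neutropenia. In the overseas hematological-malignancy study, which supplies the prior, all 5 had non-hematological DLTs. Neither study's DLT definition is given.

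**The case against.** The strongest reply is that the text is ambiguous rather than permissive. Section 3.2 sets the next dose after the DLT rate has been confirmed under 5.3.1, which contains the hematological item. Sections 5.3.2 and 11.7.3 speak of DLT evaluation being completed, not of Day 28 being reached, so a careful team could treat evaluation as open while counts are down. That reading is possible for the model update and completion. But 3.2 itself refers to the DLT rate in Cycle 1, note a places evaluation at the end of Cycle 1, and the gate in 5.3.3 is tied to the end of the 28-day period.

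Other points on that side:

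- **Section 11.2.2** keeps a subject whose treatment is postponed for a DLT and resumed at a reduced dose at the starting dose level. It covers only a DLT arising within the evaluation period. The late event is not expressly excluded, but its status is unclear.
- **Later model runs** use all evaluable subjects, so a late DLT could enter at the next update if the subject is in the MTD set. Nothing requires a rerun before more subjects are dosed.
- **Non-recovery would be visible** in the Day 22 and pre-Cycle 2 counts, and 3.2 requires the toxicity profile to be considered. What follows from that is left to judgment.
- **The illustrations are chosen cases.** After 0/3 at 90 mg the model favors 160 mg, so the first depends on going to 120 mg; that is the path described in 11.6. In the third, 160 mg remains the model's preferred dose (P(target) 0.32 against 0.09 at 120 mg) and P(over) stays below 25%; meeting a criterion leads to a comprehensive evaluation, not an automatic MTD. This is correct, but the zero-DLT criterion would still have been declared met when it was not.
- **A separate SAP** is to hold the detailed methods and analysis-set criteria and is not in the text available here. It may settle the analysis-set question. The dosing gate is a protocol rule.
- **Holding escalation for any pending subject** is stricter than the present minimum of three evaluated subjects. That is a choice, made because one pending outcome can change the recommended dose.

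**Conclusion.** The concern holds and should be corrected. Followed as written, the plan can score a subject as DLT-free, release a higher dose or meet the zero-DLT criterion while a DLT of its own definition is still open. The gap is about two weeks for most subjects and about one week for the first subject of the first cohort. One late event is enough to reverse the decision on 160 mg after the 120 mg cohort (0.44 against 0.11, limit 0.25) and to move the model's preferred second dose from 90 mg to 160 mg.

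The timing follows from the text alone. The probabilities rest on the protocol's prior, three-subject cohorts and exactly one late event. The frequency of such events is unknown, so the size of the effect on the final MTD cannot be stated.

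**What to change.** Amend 5.3.1, 5.3.3, 5.4, 11.2.2, 11.7.3 and Appendix 1 note a, and apply the same status rule to the completion criteria in 5.3.2:

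1. A subject with no other DLT whose Cycle 2 is delayed for counts is classed as DLT pending. The status ends without a hematological DLT when counts recover or Cycle 2 starts, and as a DLT when the delay passes two weeks.
2. The three-subject gate, the completion criteria and the model update use only subjects with final status. No escalation takes place while a subject in the ongoing cohort is pending.
3. The MTD analysis set counts this event as a DLT at the starting dose level.
4. A subject who progresses, withdraws or starts other therapy between Day 29 and Day 43 with unrecovered counts is not evaluable for this criterion and is replaced. Section 5.4 is extended accordingly.
5. If a DLT is established after a higher cohort has opened, the model is rerun before another subject is dosed.

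The cost is protocol wording, a wait of up to about two weeks in cohorts where Cycle 2 is delayed for counts, and an occasional replacement subject. No new procedures are needed. If 5% to 20% of subjects were delayed for counts (an assumption), the share of three-subject cohorts that would wait is 1 − 0.95³ = 14% to 1 − 0.80³ = 49%.

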5.3.2. Definition of Maximum Tolerated Dose

If any of the following completion criteria are met, the MTD will be determined based on comprehensive evaluation of the recommended dose guided by mCRM incorporating the EWOC principle, and safety and PK/PDy information of DS-3032b.

Completion criteria:

- DLT evaluation is completed in at least 15 subjects in the entire study and in at least 6 subjects in the cohort of the dose selected to be the dose for the next cohort by mCRM.
- DLT evaluation is completed in at least 6 subjects in the cohort of the dose selected to be the dose for the next cohort by mCRM, with at least 50% posterior probability for the DLT rate ranging between 16% and 33%.
- DLT evaluation is completed in at least 3 subjects in the cohort of each dose, with no DLTs reported.
- The posterior probability for the DLT rate of 33% or higher in the 90 mg cohort is at least 60%.

5.3.3. Study Treatment to Subjects in Each Cohort and Procedure for Proceeding to the Next Cohort

In the cohort of the first dose, study treatment for the second subject must be started after an at least 1-week interval from the first dose of treatment in the first subject. In the subsequent cohorts, study treatment for the next subject may be started on the following day of the start day of study treatment in the first subject.

If proceeding to the next cohort involves an increase in the dose, study treatment for the first subject in the new cohort will be started after the end of the DLT evaluation period in at least 3 subjects in the ongoing cohort. If a DLT occurs in 2 subjects before registration of the third subject, the dose for the third subject will be reviewed by using the mCRM incorporating the EWOC principle.

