4.1.3.1. Flow of Subject Registration

After obtaining written informed consent from subjects, the investigator or subinvestigator will assign a subject identification code to each of the subjects. The investigator or subinvestigator will fill out the Subject Registration Form for subjects who are assessed to be eligible for the study among the above subjects and send it by fax to the sponsor.

The sponsor will confirm the eligibility of the concerned subjects against the inclusion and exclusion criteria for this study based on the information in the received Subject Registration Form. If there are any questions about the information in the Subject Registration Form, the sponsor will immediately contact the investigator or subinvestigator for confirmation. Subjects who are assessed to be eligible for the study by the sponsor will be registered in this study and assigned a subject number.

The sponsor will immediately fax the registration confirmation form with the result of eligibility assessment to the investigator; the confirmation form should include the date of registration, subject number, and dose of the study drug for subjects assessed to be eligible, and the fact that the subject is not eligible and the reason for subjects assessed to be ineligible. The investigator or subinvestigator will explain the reason for ineligibility to subjects who are assessed to be ineligible for the study by the sponsor.

Address for sending the Subject Registration Form (the sponsor's address)

Working hours: Monday to Friday, 9:00 to 17:30
(closed on Saturdays, Sundays, and public holidays)

FAX: PPD

TEL: PPD

[figure not shown]
The investigator or subinvestigator must not prescribe the study drug before registration of subjects.

If there is any subject who has provided informed consent, but is not registered in the study, the investigator or subinvestigator will record the reason why the concerned subject has not been registered in the medical record. Such a subject will not be included in the number of subjects enrolled in this study.

If a subject who has provided informed consent, but is assessed to be ineligible for the study at the time of eligibility confirmation and for whom a Subject Registration Form has not been faxed to the sponsor, is confirmed to satisfy the eligibility criteria at a later date, the investigator or subinvestigator may fax the Subject Registration Form to the

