5.2.2. Regimen

In Subtrial A, the study drug will be administered once daily on Days 1 to 14, followed by a 14-day rest, in a 28-day cycle (14/28 schedule). Each cycle is 28 days long.

[figure not shown]
Capsules with two different strengths will be used as the study drug (30 mg and 100 mg). As a rule, subjects will orally take the study drug once daily every morning under fasting conditions. Meal consumption should be avoided from 2 hours before dosing to 1 hour after dosing.

The first dose of the study drug will be started within 7 days of the day of registration. If the study treatment is started on Day 8 or later from the day of registration, the first dose of the study drug should be started only after the subject's eligibility has been confirmed again before the start of the study treatment (see "[Section 6.2 Study Procedures before Registration of Subjects](#)"). Day 1 of Cycle 3 and subsequent cycles may be rescheduled within + 3 days of the originally scheduled date. If the schedule of Day 1 is changed, all subsequent scheduled dates will be changed accordingly.

If a subject vomits after taking the study drug, it is not allowed to take another dose of the study drug on the same day.

Other dosing schedules (Subtrials B, C, and D) will be assessed if it becomes necessary in order to evaluate the safety of DS-3032b. Dosing schedules in each subtrial are shown in "[Figure 5.2-1 Dosing Schedules in Each Subtrial](#)."

Figure 5.2-1: Dosing Schedules in Each Subtrial

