6.2. Study Procedures before Registration of Subjects

The following examinations and assessments, etc. will be performed and the results will be recorded in the case report form.

Data collected before informed consent can also be used if they are obtained within the acceptable limit for each item.

If the study treatment is started on Day 8 or later based on the day of registration defined as Day 0, the patient's eligibility should be assessed again on the preceding day or the start day (before administration) of study treatment.

1. Items confirmed after informed consent obtainment but before the start of subject registration

- Date of informed consent to participate in this study
- Subject identification code
- Date of birth
- Sex
- Race
- Height
- Eligibility
- Medical history and complications

Symptoms that are expressed at the time of informed consent will be recorded as complications.

Regarding medical history, only symptoms/diseases that were cured at the time of informed consent and are considered necessary to be reported at the investigator's or subinvestigator's discretion will be recorded.

- Information on the underlying disease (AML)

Collect data on the date of the first diagnosis, the World Health Organization (WHO) classification, and the date of relapse.

- Prior therapy

The following items will be confirmed:

- Medications for AML: Drug name, stop date, best response, number of courses
- Radiation therapy for AML: Purpose, location, stop date, best response
- Hematopoietic stem cell transplantation: Details, date of transplantation
- Others: Details, stop date
- Assessment of SAEs

Information on SAEs that occur from after informed consent to before the first dose of the study drug will be collected. Information on non-SAEs is not subject to collection during this period.

2. Items performed within 14 days before the day of registration (screening tests)

*Performed on a day as close as possible to the day of registration

- Vital sign measurement

Axillary body temperature, pulse rate, and systolic and diastolic blood pressure will be measured at rest.

- Body weight measurement
- ECOG PS assessment

Subject's general condition will be assessed in accordance with the criteria provided in "[Appendix 2](#)."

- 12-lead ECG measurement (including evaluation of QTcF)

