15.6. Provision of New Information Affecting the Conduct of the Study

If any information that may affect the subject’s willingness to continue participation in the study is obtained, the investigator or subinvestigator will promptly inform the subject and confirm the subject’s willingness to continue participation in the study. The investigator or subinvestigator will also document (eg, in the medical record) the date of explanation, the person who has given the explanation, the details of the explanation, the subject’s decision, and the date of confirmation. The investigator will also promptly revise the consent form and subject information form, as necessary, and submit them to the sponsor. The investigator will also report the revised forms to the head of the study center and request review and approval by the IRB. For subjects who are already participating in the study, their consent to remain in the study should be obtained in the same manner as the above-mentioned informed consent procedure using the revised consent form and subject information form. A copy of the said consent form and subject information form will be provided to the subject. The investigator or subinvestigator will document (eg, in the original consent form or medical record) that a copy of the consent form and subject information form have been provided to the subject.

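### The dose review after two DLTs stops at the third subject's registration rather than first dose, so a second DLT in between triggers no required review

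*Combined protocol and SAP*

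**What the plan says.** Section 5.3.3 sets a safeguard inside a cohort: "If a DLT occurs in 2 subjects before registration of the third subject, the dose for the third subject will be reviewed" using the mCRM with EWOC. Four other provisions decide what that means in practice.

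- **Dose assignment.** Section 4.1.3.1 has the sponsor return a form after registration; for eligible subjects, "the confirmation form should include the date of registration, subject number, and dose of the study drug". Drug may not be prescribed before registration.
- **Time to first dose.** Section 5.2.2: "The first dose of the study drug will be started within 7 days of the day of registration". A later start is allowed, with no stated maximum: "If the study treatment is started on Day 8 or later from the day of registration", eligibility must be confirmed again first. Section 6.2 describes the same step: "eligibility should be assessed again on the preceding day or the start day (before administration) of study treatment". Neither mentions the dose.
- **Completion criterion at 90 mg.** The fourth criterion in Section 5.3.2 is "The posterior probability for the DLT rate of 33% or higher in the 90 mg cohort is at least 60" percent. No such criterion is written for 120 or 160 mg.
- **Model runs.** Section 11.7.3 schedules the posterior update after three evaluated subjects per cohort, in principle, and adds: "The EWOC principle will apply from the third cohort".

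**The concern.** The sentence exists to stop a third subject from starting at a dose where both predecessors had a DLT. That protection is possible until the first capsule is taken, yet the trigger ends at an administrative step that may come a week or more earlier. The other timing rules in Section 5.3.3 (the one-week interval, the next-day start, the start of a new cohort) are all tied to study treatment. This one is tied to registration.

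Followed literally, the plan lets a registered but undosed subject begin at the assigned dose after 2/2 DLTs without the review the section sets up for that situation. The stake is the safety of that one subject. The MTD analysis is not affected.

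**Working it through.** **1. Is there another required dose review?** The routine model update waits for three evaluated subjects, which is too late for subject 3. Section 5.5.1 deals with the subject who had the toxicity. Section 9.5.2 requires 24-hour reporting of SAEs, but a DLT need not be an SAE: Section 5.3.1 counts Grade 2 or higher events that prevent 75% of Cycle 1 doses. Section 15.9 lets the sponsor suspend the study at its discretion. Section 15.6 covers information that may affect willingness to continue ("the investigator or subinvestigator will promptly inform the subject and confirm") and does not concern the dose. None requires a dose review for this subject.

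**2. What would the review conclude?** The inputs are from Sections 11.7.1 and 11.7.2: logit π(d) = log α + β log(d/160), with (log α, log β) bivariate normal, means (−1.8999, 1.3484), SDs (2.2792, 1.3727), correlation −0.3157. Grid integration gives prior medians of 3.1% at 120 mg and 13.0% at 160 mg, which reproduces the plan's 3% and 13%. The posteriors with 2/2 DLTs at the current dose are:

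| Data | Dose | P(π > 33%) | P(16% < π ≤ 33%) |
|---|---|---|---|
| 2/2 at 90 | 90 | 0.906 | 0.072 |
| 0/3 at 90, 2/2 at 120 | 90 | 0.302 | 0.329 |
| | 120 | 0.610 | 0.276 |
| 0/6 at 90, 2/2 at 120 | 90 | 0.101 | 0.305 |
| | 120 | 0.428 | 0.370 |
| 0/3 at 90, 0/3 at 120, 2/2 at 160 | 120 | 0.073 | 0.187 |
| | 160 | 0.752 | 0.181 |

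Section 5.3.3 calls for EWOC in this review, while Section 11.7.3 starts EWOC at the third cohort, so both readings are shown, with the EWOC limit at 25%.

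- *160 mg as third cohort:* EWOC applies on either reading, and the recommendation falls to 120 mg.
- *120 mg after 0/3:* with EWOC no planned dose passes, because 90 mg is at 30%. Without it, 90 mg has the higher target probability (0.329 against 0.276). The assigned 120 mg is refused either way.
- *120 mg after 0/6:* with EWOC the dose falls to 90 mg; without it, 120 mg stays (0.370 against 0.305). The result depends on the reading.
- *90 mg:* 0.906 exceeds the 0.60 completion criterion.

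**3. How often would it happen?** The documents give no DLT onset times, so this rests on assumptions: onset uniform over the 28 days of Cycle 1, and subject 3 registered on day r = 7, 14 or 21. Subject 1 starts on day 0 and subject 2 on day s, with s = 7 in the first cohort and s = 1 later (the shortest intervals Section 5.3.3 allows). With gap g and DLT rate p:

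F(t) = min(t/28, 1) × min((t − s)/28, 1); missed fraction = p² × [F(r + g) − F(r)].

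Example with s = 1, r = 21, g = 7, p = 0.20: F(28) = 1 × 27/28 = 0.964; F(21) = 0.75 × 20/28 = 0.536; the difference is 0.429; 0.04 × 0.429 = 1.7%.

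| Gap | p | First cohort | Later cohorts |
|---|---|---|---|
| 1 day | 20% | 0.04–0.18% | 0.07–0.21% |
| 3 days | 20% | 0.15–0.58% | 0.25–0.67% |
| 7 days | 20% | 0.5–1.5% | 0.7–1.7% |
| 7 days | 33% | 1.4–4.1% | 1.9–4.7% |
| 7 days | 50% | 3.1–9.4% | 4.5–10.7% |
| 14 days | 20% | 1.5–2.5% | 1.9–2.9% |

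**The case against.** The best case for leaving the text alone is that harm needs several people to know of 2/2 DLTs and still dose. Beyond SAE reporting and the sponsor's power to suspend, Section 5.9 obliges the investigator to maximize safety throughout the study period, which Section 6.1 starts at consent. Withdrawal criterion 8 in Section 5.6 lets the investigator stop a subject at any time, and exclusion 20 is available at a late-start re-check. All of this is true, but these are discretionary and none is a dose review. The study is also multicenter, so the third subject's investigator may not have seen either DLT.

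At 90 mg the completion criterion is met after 2/2, and nothing ties it to a scheduled model run. That largely answers the 90 mg case, although the plan does not say the posterior must be computed at that moment. The remaining gap is at 120 and 160 mg.

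There the event is rare by the plan's own model. The predictive chance of 2/2 DLTs is 1.6% at 120 mg after 0/3, and 4.5% at 160 mg after 0/3 and 0/3. Multiplied by the later-cohort fractions for a 7-day gap (0.179 to 0.429), that gives 0.3% to 0.7% and 0.8% to 1.9% of cohorts. With 9 to 24 subjects it will probably never happen. This stands, and it limits the point to minor.

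Two further cautions also stand. The hematological DLT, a Cycle 2 delay of more than 2 weeks, shows itself after day 28, so uniform onset overstates the gap frequency for that type. In some cases (2/2 at 90 mg, and 2/2 at 120 mg after 0/3 with EWOC) no planned dose passes, so the review ends in a sponsor decision. The existing rule already has that consequence for a subject not yet registered.

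**Conclusion.** The concern holds, as a minor one. The required review stops at registration, the dose is assigned there, and no other provision requires a dose review before the third subject's first dose. The model refuses the assigned dose after 2/2 DLTs at 160 mg (75% probability of exceeding a 33% DLT rate) and at 120 mg after 0/3 (61%), on either reading of the EWOC text. At 120 mg after 0/6 (43%) the outcome depends on the reading. The posteriors rest only on the stated model and prior; the gap frequencies rest on the assumed onset and registration times. Under those assumptions the event is uncommon at acceptable DLT rates and most frequent when the dose is too toxic, which is when the rule is needed.

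**What to change.** In Section 5.3.3, end the trigger at the first dose of the third subject instead of at that subject's registration. In Section 4.1.3.1, add: *The dose on the confirmation form remains subject to the review in Section 5.3.3 until the first dose.*

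Two clarifications would help but are not needed for this fix: state that the Section 5.3.3 review applies the EWOC limit in every cohort, and state whether it also covers a later subject who would start at that dose before the three-subject model run.

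The cost is one phrase and one sentence in an amendment, with no extra patients or tests. The added reviews equal the gap frequency: with 7-day gaps, at most 1.7% of cohorts at a 20% DLT rate and 4.7% at 33%. All two-DLT reviews together cannot exceed p² (4% and 11%). The model input is a complete 2/2, so no partial follow-up has to be handled. The downside is an occasional short wait for the third subject, and a sponsor decision when no planned dose passes.
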